8.1.6 Relationship to the study drug(s) and/or clinical trial procedure

The investigator is to determine whether there is a reasonable causal relationship between the occurrence of the AE and exposure to the study drug(s) and/or clinical trial procedure. Medical judgment should be used to determine the relationship, considering all relevant factors, including pattern of reaction, temporal relationship, positive de-challenge or re-challenge, relevant medical history, and confounding factors such as co-medication or concurrent diseases.

The expression "reasonable causal relationship" is meant to convey in general that there are facts or arguments to suggest a causal relationship (International Conference on Harmonization (ICH) E2A, section IIIA 1).

The relationship assessment for an AE is to be completed using the following definitions as a guideline for all adverse events occurring during clinical trials conducted or sponsored by GALDERMA:

Reasonable possibility:

According to the reporting investigator, there is a reasonable possibility (i.e. suggestive evidence or arguments) that there is a causal relationship irrespective of the dose administered between:

The study drug (investigational product, active comparator, or vehicle, etc.) and the AE,

Protocol N° RD.03.SPR.113322

version Final dated 10-FEB-2017

Page 67 of 106 CONFIDENTIAL

• The clinical trial protocol procedure (e.g., UV-induction, biopsy, xylocaine injection, blood test or intraocular pressure measurement, ancillary products provided by the sponsor, such as moisturizers, etc. and the AE.

The Investigator has to complete these 2 causality assessments on the AE form.

No Reasonable Possibility:

No suggestive evidence or arguments can be identified regarding a causal relationship between the investigational product or the clinical trial protocol procedure and the AE.

8.2 Reporting procedures

8.2.1 Procedures for reporting adverse events

The collection of AEs is from the time that a subject signs the ICF to their final trial visit.

At each post-baseline visit, the investigator (or sub-investigator) will enquire about adverse events using an open question taking care not to influence the subject's answer (e.g., "Have you noticed any change in your health since the last visit?"). Direct questioning and examination will then be performed as appropriate.

Any AE occurring during the AE reporting period, whether it is related to the study drug or not, will be recorded immediately in the source document, and described in the Adverse Event Form with the date of onset, severity, relationship to the study drug), and outcome, without omitting any requested and known information. Additional information will be requested under certain circumstances. Adverse Events (AEs) assessed as related to the treatment will be monitored until they are completely or satisfactorily resolved. Other AEs will be monitored until the last visit if they are not resolved or satisfactorily resolved.

Adverse events assessed as related to the treatment or study procedure will be monitored until they have resolved or reached a stable condition. Other AEs will be monitored until the last visit if they have not resolved or reached a stable condition. The investigator will obtain and maintain in the subject's files all pertinent medical records, information and medical judgment from colleagues who assisted in the treatment and follow-up of the subject. If necessary, the investigator will contact the subject's personal physician or hospital staff to obtain further details. For SAEs (see section 8.2.2) and pregnancies (see section 8.3), the Sponsor is to be informed

Protocol N° RD.03.SPR.113322

version Final dated 10-FEB-2017

Page 68 of 106 CONFIDENTIAL

immediately by e-mail/fax. The event must be reported by fax or sent by e-mail to the Sponsor within 24 hours of receipt of the information (contact details in section 8.2.2).

8.2.2 Procedure for reporting a serious adverse event

For an SAE occurring during the period of the clinical trial, regardless of whether it is related to the treatment or not, and of whether it is expected or not, the investigator must do the following:

- 1. Take prompt and appropriate medical action, if necessary. The safety of subject is the first priority.
- 2. Ensure that the event is classified as an SAE. Immediately (no later than 24 hours) inform the Sponsor of the event by email/ fax/, and discuss further actions to be taken:

	GALDERMA R&D
Name	
Title	
Address	
Tel. during office hours	
Tel. outside office hours	
Fax	
Email	[contact]

3. Print and complete the Serious Adverse Event form (available in the eCRF system as PDF document). Fax or send by email the completed form, accompanied any other relevant information or anonymized medical records (e.g., laboratory test results) within 24 hours of

Protocol N° RD.03.SPR.113322

version Final dated 10-FEB-2017

Page 69 of 106 CONFIDENTIAL

receipt of this information to the sponsor (see contact details above). The demographics, medical history, drugs/therapies forms, and adverse event pages of the eCRF must be completed and available for review in the eCRF system at the time of the report.

- 4. **Monitor and record the progress of the event until it resolves** or reaches a clinically stable outcome, with or without sequelae. For all additional follow-up evaluations, fax or send by e-mail all additional follow-up information on the SAE to the sponsor (see contact details above) within 24 hours of receipt of the updated information. SAEs will be monitored until the Investigator and Sponsor agree that the event is satisfactorily resolved.
- Obtain and maintain in his/her files all pertinent medical records, information, and medical judgments from colleagues who assisted in the treatment and follow-up of the subject. If necessary, contact the subject's personal physician or hospital staff to obtain further details
- 6. **Inform the sponsor of the final outcome of the event**. Send a revised or updated SAE form and AE form, if appropriate.
- 7. Prompt notification of SAEs by the investigator to GALDERMA is essential so that legal obligations and ethical responsibilities towards the safety of subjects are met. GALDERMA has a legal responsibility to notify both the local regulatory authority and other regulatory agencies about the safety of a product under clinical investigation. GALDERMA will comply with country specific regulatory requirements relating to safety reporting to regulatory authorities, IRBs/IECs and investigators. Investigator safety reports are prepared for Suspected Unexpected Serious Adverse Reactions (SUSARs) according to local regulatory requirements and GALDERMA policy and are forwarded to investigators as necessary. An investigator who receives an investigator safety report describing an SAE(s) or other specific safety information (e.g., summary or listing of SAEs) from GALDERMA will notify the IRB/IEC, if appropriate according to local requirements.
- 8. Comply with the applicable regulatory requirements related to the reporting of SAEs to your IRB/EC.

8.2.3 Procedure for suspected allergic contact reaction

This is a general procedure and further details can be discussed with the sponsor.

- Stop the trial product
- Take a picture of the affected area and the non-affected surrounding skin
- Document the event and report it immediately to the sponsor by email/fax, within 24 hours of receipt of the information as described in section 8.2.2.

Protocol N° RD.03.SPR.113322

version Final dated 10-FEB-2017

Page 70 of 106 CONFIDENTIAL

In case of suspicion of allergic contact dermatitis

- 1. After all signs and symptoms have resolved and after a minimum of two weeks from last dose application, a re-challenge test with the assigned trial product will be performed.
- 2. Ensure the subject has not been under any treatment with corticosteroids or antihistamines, regardless of the route of administration, the week before testing.
- 3. Ensure that the skin on the back has not been exposed to the sun or artificial ultraviolet sources the week before testing.
- 4. Apply an appropriate quantity of the assigned trial product to fill the cupule of the test chamber on the skin of the upper back on either the right or left side of the center line (or the inner forearm if the back cannot be tested). If no test chamber is available on-site, patch test units will be provided. It may be preferable to perform the test under semi-occlusive conditions depending on the irritant potential of the trial product and the intensity of the reaction that was observed. The method to be used will be discussed with the sponsor.
- 5. Choose a skin site that was not previously involved in the inflammatory skin reaction.
- 6. Cover it for 48 hours with a hypoallergenic tape.
- 7. Subject should be informed about avoiding exercise, showers, application of toiletries products, etc. to keep the test system dry
- 8. After 48 hours, remove the tests and evaluate the site:
 - At approximately 30 minutes after patch test removal (1st reading) and,
 - 24 to 48 hours later (i.e. 72 or 96 hours after application) (2nd reading).
 - A facultative 3rd reading may be performed 96 to 120 hours later (i.e. 6 to 7 days after application of the patch) if the overall assessment so far equivocal or if asked by the sponsor.
 - Pictures of the tested areas will be taken systematically at each reading and properly documented.

Duration of trial	1 st Reading	2 nd Reading	3 rd reading
product application			(optional)
			(optional)

Protocol N° RD.03.SPR.113322

version Final dated 10-FEB-2017

Page 71 of 106 CONFIDENTIAL

48 hours	48 hours after trial	72 to 96 hours after trial	6 or 7 days after trial
	product application (30	product application (24 to	product application (96 to
	minutes	48 hours after patch test	120 hours after patch
	after patch test removal)	removal)	removal)

9. Refer to the scoring system (Spiewak, R. 2008^{1.17}) used by the International Contact Dermatitis Research Group (ICDRG) to assign a score at each reading:

Score	Morphology	Interpretation
-	No skin changes in the tested area	Negative
?	Faint, non-palpable erythema	Doubtful reaction
+	Palpable erythema (moderate edema or infiltrate), papules not present or scarce, vesicles not present	Weak positive reaction
++	Strong infiltrate, numerous papules, vesicles present	Strong positive reaction
+++	Erythema, infiltration, confluent vesicles, bullae or ulceration	Extreme positive reaction
ir	Inflammation sharply limited to the exposed area, lack of infiltrate, small petechiae, pustules, and efflorescence other than papules and vesicles	Irritant reaction
Nt		Not tested

10. At last reading, the investigator will provide an assessment regarding a possible sensitization reaction using the following scale:

Sensiti	zation Reaction
0	Negative (absence of reaction or might be irritant reaction)
1	Equivocal

Protocol N° RD.03.SPR.113322

version Final dated 10-FEB-2017

Page 72 of 106 CONFIDENTIAL

2	Positive

- 11. Report the results from the re-challenge test as directed by the sponsor and document with photographs.
- 12. In case of absence of reaction, the subject may resume treatment if appropriate
- 13. If the re-challenge is positive or equivocal, notify the sponsor immediately. Except specific situations, a new series of patch test will be initiated as directed by the sponsor (with individual ingredients at different concentrations if applicable, and possibly negative and positive controls) after a minimum of additional two weeks (but not later than 6 months) and after all signs and symptoms have resolved. The patch tests will be placed on the subject's back (or the inner forearm if the back cannot be tested) distant from the site of the re-challenge test (e.g., the left upper back skin if the re-challenge test was done on the right side). Follow the same procedure for the patch test as for the re-challenge.
- 14. In case of suspicion of immediate contact skin reaction (such as urticaria)

A case by case approach will be applied and the procedure to follow will be discussed with the sponsor.

8.3 PROCEDURES FOR REPORTING PREGNANCIES

Any pregnancy occurring during clinical trials, where the fetus could have been exposed to the investigational product(s), must be followed-up until outcome in order to ensure the complete collection of safety data on *GALDERMA* product.

If a subject becomes pregnant, the Investigator is to do the following:

- 1. Withdraw the subject from the clinical trial
- 2. Complete all appropriate visit evaluations and CRF pages.
- 3. **Immediately (no later than 24 hours) contact the Sponsor** to inform them of the pregnancy occurrence and discuss further steps to be taken.
- 4. **Complete, as fully as possible, the pregnancy surveillance form Part I:** History and start of pregnancy provided by the CRA at the beginning of the clinical trial, as fully as possible. Fax or send by email this pregnancy form along with the Exit form within 24 hours of receipt of the information to the Sponsor.

Protocol N° RD.03.SPR.113322

version Final dated 10-FEB-2017

Page 73 of 106 CONFIDENTIAL

	GALDERMA R&D
Name	
Title	
Address	
Tel. during office hours	
Tel. outside office hours	
Fax	
Email	[contact]

- 5. Monitor and record the progress of the pregnancy until its outcome. Contact the subject's regular physician (general practitioner or gynecologist) or hospital staff to obtain further details and ask regular follow-up information.
- 6. **Inform the Sponsor of the progress by tri-monthly updates up** to the final outcome of the pregnancy. For all the additional follow-up evaluations, fax or send by e-mail the additional follow-up information to the sponsor within 24 hours of receipt of the information. If the subject can no longer be reached (lost to follow-up), documentation of the non-response/contact with two phone calls and a letter (certified with return receipt) is required.

At outcome of pregnancy, complete as fully as possible the pregnancy surveillance form – Part II: Course and outcome of pregnancy, as full as possible. Inform the Sponsor by email/ fax, then fax or send by e-mail this pregnancy form to the Sponsor within 24 hours of receipt of the information.

7. If the pregnancy leads to an abortion (voluntary abortion, spontaneous abortion or therapeutic abortion), *in utero* death or congenital anomaly, follow the procedure for declaration of an SAE (see Section 8.2.2).

Protocol N° RD.03.SPR.113322

version Final dated 10-FEB-2017

Page 74 of 106 CONFIDENTIAL

9. STATISTICAL METHODS PLANNED

9.1 STATISTICAL AND ANALYTICAL PLANS

A Statistical Analysis Plan (SAP) will be developed as a separate document. The SAP will contain a more detailed and technical description of specific data conventions, calculations and of statistical procedures for executing the analyses that are specified in the sections of the clinical trial protocol below. The SAP will be finalized prior to database lock and unblinding.

Any change made to the finalized SAP will be documented in the clinical trial report.

The purpose of the trial is to evaluate the efficacy of Ivermectin 1% topical cream associated with Doxycycline 40 mg Modified release (MR) capsules versus Ivermectin 1% topical cream associated with Placebo in the treatment of severe Rosacea.

The Safety and Patient Reported Outcomes (PRO) will be also evaluated.

9.1.1 Variables to be statistically analysed

The following variables will be analysed:

9.1.1.1 Primary efficacy variable

The primary endpoint is the percent change from Baseline in Inflammatory Lesion count at Week 12.

9.1.1.2 Secondary efficacy variables

The secondary efficacy endpoints are:

- Percent change from Baseline in Inflammatory Lesion count at each intermediate visit
- CEA at each post-Baseline visit: % of subjects across scores
- IGA at each post-Baseline visit: % of subjects across scores
- Stinging/burning at each post-Baseline visit: % of subjects across scores
- Percent change from Baseline (medical history) in terms of flushing count per week over 12 weeks
- Change from Baseline (medical history) in terms of flushing severity score per week over 12 weeks
- Global improvement in rosacea at the last visit: % of subjects across scores

9.1.1.3 Exploratory efficacy variable

One exploratory endpoint is planned to be analyzed:

Protocol N° RD.03.SPR.113322

version Final dated 10-FEB-2017

Page 75 of 106 CONFIDENTIAL

The global assessment of Ocular signs and symptoms at each post-Baseline visit: % of subjects across scores

9.1.1.4 Safety variables

- Incidence of adverse events
- Incidence of serious adverse events

9.1.1.5 Patient Reported Outcomes (PRO)

- DLQI questionnaire at Baseline and the last visit
- EQ-5D-5L questionnaire at Baseline and last visit
- WPAI:GH questionnaire at Baseline and last visit
- Subject Satisfaction Questionnaire at last visit

9.1.2 Populations analysed, evaluability and limitations / evaluation of Bias

The statistical analyses will be performed based on the following subject populations:

9.1.2.1 The Per Protocol efficacy population (PP)

This population will consist of all enrolled and randomised subjects, except subjects who have major deviations from the protocol. Major deviations will be defined during a data review meeting after data entry and before unblinding the clinical trial treatment. Major protocol deviations will be considered as having a possible effect on the interpretation of primary efficacy results and may include: inclusion criteria not respected, non-available efficacy assessment, interfering therapy at inclusion, etc. The primary efficacy endpoint will be analysed based on this population.

9.1.2.2 The Intent-to-Treat efficacy population (ITT)

This population will consist of the entire population enrolled and randomised (i.e. assigned a kit number). The ITT population will be used for all variables except the safety variables.

9.1.2.3 The Safety population (All subject treated [APT])

This population will consist of the Intent-to-Treat population, after exclusion of subjects who never used the treatment with certainty based on monitoring report. The APT population will be only used for the safety variables (AEs).

9.1.2.4 Missing values

The last observation carried forward (LOCF) method will be used to impute missing values of Inflammatory Lesion count, CEA, IGA and Stinging/burning sensation. If no post-baseline data

Protocol N° RD.03.SPR.113322

version Final dated 10-FEB-2017

Page 76 of 106 CONFIDENTIAL

are available, baseline will be carried forward. Thus, the number of subjects will not vary at each visit. The other missing values will not be replaced (observed data).

9.1.3 **Data presentation and graphics**

All continuous data will be summarized using usual statistics: number of values, mean, median, standard deviation, minimum and maximum, and by frequency distribution (n, %) for qualitative data. For ordinal data, both frequency distribution and usual statistics will be presented. All tables will be presented by clinical trial treatment and by visit (when applicable).

Therapies that have been stopped before the baseline visit will be presented as prior therapies. Those reported at screening or starting between screening and baseline visits and still continuing after baseline will be classified as concomitant therapies.

The adverse events will be descriptively summarized (n, %) for the safety population (APT). The adverse events will be descriptively summarized (n, %) by relationship to clinical trial treatments within System Organ Class (SOC) and preferred term (MedDRA). Subjects will be descriptively summarized (n, %) by intensity (*i.e.* mild, moderate and severe) of adverse events, SOC and preferred terms. Deaths and serious adverse events will be reported as well as withdrawals due to adverse events. A subject will be counted only once per System Organ Class (SOC) and only once per preferred term even if more than one occurrence of an event was reported within a SOC or preferred term. In the summary by categories of intensity, the adverse event with the highest intensity will be used. The subject will be counted only once per SOC (highest intensity whatever the AE within the SOC) and once per preferred term (highest intensity whatever the AE within the preferred term).

9.1.4 Statistical analyses

Any changes of the statistical analyses decided after the database lock will be justified and documented.

The definition of the populations will be finalized after a blind data review meeting, during which the distribution of subjects per site will be reviewed. In case of too small sites or in case of severe unbalance between the size of sites, some sites may be combined, e.g. per geographical area, to form analysis-center for purpose of stratification of the statistical analyses.

The primary objective of this study will be to demonstrate the superiority of the Ivermectin 1% topical cream associated with Doxycycline 40 mg MR capsules compared to versus Ivermectin 1% topical cream associated with Placebo, in terms of Inflammatory Lesion count at week 12.

The primary efficacy endpoint will be analyzed by using the Cochran-Mantel-Haenszel (CMH, FREQ procedure from SAS®) statistic, stratified by center (or analysis-center) after ridit

Protocol N° RD.03.SPR.113322

version Final dated 10-FEB-2017

Page 77 of 106 CONFIDENTIAL

transformation with the row mean difference statistics, testing the hypothesis of equality on ITT/LOCF population. PP analysis will also be performed to assess the robustness of the results obtained on ITT/LOCF population. The p-values will have to be inferior to 0.05 at week 12.

The secondary efficacy variables, questionnaires will be analyzed similarly as primary analyses on appropriate population.

The subject characteristics (disposition, previous and concomitant therapies, study treatments duration/ compliance, demographics, baseline characteristics,...), lesion counts and adverse event(s) will only be summarized descriptively, on appropriate population.

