4.2.1 Inclusion criteria

In order to be eligible for the clinical trial, the subject must meet all of the following inclusion criteria:

- Male or female subject age ≥ 18 years or older;
- 2. Subject with a minimum of 20 but not more than 70 inflammatory lesions (papules and pustules) of rosacea on the face at Baseline visit;
- 3. Subject with severe rosacea with papulopustular lesions (according to the Investigator's Global Assessment, IGA score rated 4);
- 4. Female Subject of childbearing potential must have a negative urinary pregnancy test (UPT) at baseline visit (UPT should have a sensitivity of 25 IU/L or less). They must agree to use/continue a highly effective and approved contraceptive method(s) for the duration of the study and at least 4 weeks after the last study drug(s) use. A highly effective method of contraception being defined as:
 - bilateral tubal ligation;
 - combined oral contraceptives (estrogens and progesterone) or implanted or injectable contraceptives with a stable dose for at least 1 month prior to Baseline visit:
 - hormonal intra-uterine device (IUD) inserted at least 1 month prior to Baseline visit;
 - vasectomized partner for at least 3 months prior to Baseline

OR

Protocol N° RD.03.SPR.113322

version Final dated 10-FEB-2017

Page 33 of 106 CONFIDENTIAL

- 5. Is of non-childbearing potential, defined as post-menopausal (absence of menstrual bleeding for one year prior to clinical trial entry without any other medical reasons), hysterectomy or bilateral oophorectomy prior to clinical trial entry.
- 6. Willing and able to comply with all of the time commitments and procedural requirements of the clinical trial protocol. In particular, subject must adhere to the visit schedule, concomitant therapy prohibitions, and must be compliant with the treatment at study visits.
- 7. Understand and sign an Informed Consent Form (ICF) and photo consent (when appropriate) at screening, prior to any investigational procedures being performed.
- 8. Apprised of the Health Insurance Portability and Accountability Act (HIPAA), if in the US, or the Personal Information Protection and Electronic Documents Act (PIPEDA) if in Canada [or the equivalent in other regions] and is willing to share personal information and data, as verified by signing a written authorization at the screening/baseline.

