7.1 EFFICACY ASSESSMENTS

7.1.1 Inflammatory Lesion Count

The evaluator will perform inflammatory lesion count on facial papules and pustules of rosacea at baseline and then at each visit.

Inflammatory lesions are defined as follows:

- Papule A small, solid elevation less than one centimeter in diameter
- Pustule A small, circumscribed elevation of the skin, which contains yellow white exudates.

Papules and pustules will be counted separately on each of the five facial regions (forehead, chin, nose, right cheek and left cheek). **Nodules** (defined as a circumscribed, elevated, solid lesion more than 1.0 cm in diameter with palpable depth) **will not be included in the count of inflammatory lesions**, and subjects are not eligible if they have more than 2 nodules on the face at screening/baseline visit.

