6.3 EFFICACY ANALYSES

6.3.1 Primary efficacy analyses

The primary objective of this study was to demonstrate the superiority of the IVM/Doxy compared to IVM/Placebo, in terms of percent change from baseline in inflammatory lesion count at week 12.

The primary efficacy endpoint will be analyzed by using the Cochran-Mantel-Haenszel (CMH, FREQ procedure from SAS®) statistic, stratified by center (or analysis-center) after ridit transformation with the row mean difference statistics, testing the hypothesis of equality on ITT/LOCF population. PP analysis will also be performed to assess the robustness of the results obtained on ITT/LOCF population. The p-values will have to be inferior to 0.05 at week 12.

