14.2. Efficacy analyses

14.2.1. Primary efficacy analyses

Table 15. Inflammatory lesions: % change from baseline at week 12 (ITT/LOCF)

	IVM + Doxycycline	IVM + Vehicle	p-value (1)
Week 12 (ITT/LOCF)			XXX
N			
Mean ±SD			
Median			
Min,Max			
Week 12 (PP)			XXX

⁽¹⁾ p-value of CMH test based on ridit scores stratified by analysis-center.

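### The primary CMH test adjusts for centre but not for baseline lesion count; it is valid, but may give up a little power that a rank-covariance form of the same test would recover

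*Protocol*

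**What the plan says.** Protocol 9.1.1.1 defines the endpoint: "The primary endpoint is the percent change from Baseline in Inflammatory Lesion count at Week 12". Protocol 9.1.4 tests it with the CMH "statistic, stratified by center (or analysis-center) after ridit" transformation, and SAP 6.3.1 repeats this: "stratified by center (or analysis-center) after ridit transformation with the row mean difference statistics". The footnote to SAP Table 15 agrees: "p-value of CMH test based on ridit scores stratified by analysis-center". The ITT/LOCF result decides, and the PP result is the robustness check. SAP 6.3.2 carries the method over to Weeks 4 and 8 (Table 16).

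Baseline count is known for everyone. Protocol 7.1.1 states "The evaluator will perform inflammatory lesion count on facial papules and pustules of rosacea at baseline and then at each visit", and the flow chart (5.4) puts that first count at Visit 1, before a kit is assigned. Eligibility requires "Subject with a minimum of 20 but not more than 70 inflammatory lesions (papules and pustules) of rosacea on the face at Baseline visit" (4.2.1).

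Neither document uses baseline count as a covariate or stratum in any primary, secondary or sensitivity analysis. Protocol 6.1.2 describes 1:1 allocation in blocks and mentions no stratification by baseline count. SAP Table 14 only describes it.

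**The concern.** Baseline count enters the primary analysis only as the denominator of the percent change. Dividing by it removes its influence only if Week 12 counts are proportional to the observed baseline count. Two features make exact proportionality doubtful: the baseline is a single count with counting error, and subjects are selected on that same count between 20 and 70 (a 3.5-fold range). If proportionality fails, percent change remains correlated with baseline. The centre-stratified ranks then carry variation that could be explained, and a chance imbalance in baseline count feeds into the result. This is the one test on which the trial's conclusion rests, so an efficiency gain that needs no extra patients is worth considering.

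**Working it through.** **1. The plan's own figure.** Inputs from protocol 9.2: difference 15 points, SD 35, power 90%, 15% exclusions; two-sided 0.05 from SAP 6.

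n per arm = 2 × [(1.960 + 1.282) × 35/15]² = 114.4, against 114 stated (115 if rounded up). Then 114/0.85 = 134.1, so 135. The figure stands, and it does not rely on baseline adjustment.

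**2. Which n applies.** The primary set is ITT with LOCF, and baseline is carried forward if nothing follows (protocol 9.1.2.2 and 9.1.2.4). All randomised subjects are analysed, so the relevant n is 135 per arm. Then δ/SE = 15 / [35 × √(2/135)] = 3.521, and power = Φ(3.521 − 1.960) = 94.1%.

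**3. Formula gain from adjustment.** Let rho be the within-arm correlation of baseline count with percent change. It is an assumption. Adjustment multiplies the SD by √(1 − rho²), so power = Φ(3.521/√(1 − rho²) − 1.960).

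| assumed rho | variance removed | power, SD 35 | power, SD 39.9 |
|---|---|---|---|
| 0 | 0% | 94.1% | 87.0% |
| 0.1 | 1% | 94.3% | 87.4% |
| 0.2 | 4% | 94.9% | 88.3% |
| 0.3 | 9% | 95.8% | 89.9% |

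SD 39.9 is the top of the historical range in protocol 9.2.1. At SD 35 the gains are about 0.2, 0.8 and 1.7 points.

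**4. Simulated lesion counts.** Assumptions: 270 subjects in 9 analysis-centres of 30; log-normal latent severity (median 34, log-SD 0.45); observed baseline Poisson with log-error SD 0.2, kept if 20 to 70; Week 12 count Poisson with mean proportional to a power of severity, frailty SD 1.1 and log treatment effect −0.5. There were 6,000 replicates per row in run A, with a Monte Carlo error of about 0.4 points per rate. Both tests were applied to the same simulated trials. Run B is a repeat.

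| Week 12 count versus severity | rho (approx.) | run A, planned / adjusted | run B, planned / adjusted |
|---|---|---|---|
| proportional | not tabulated | 87.4 / 87.5% | 88.4 / 88.4% |
| half-proportional | −0.15 | 87.9 / 88.5% | 87.3 / 87.2% |
| unrelated | −0.24 | 87.3 / 88.8% | 87.8 / 89.1% |
| more than proportional | +0.15 | 83.3 / 83.9% | 84.2 / 85.1% |
| no treatment effect | – | 5.1 / 5.2% | 4.6 / 4.8% |

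Gains run from about 0 to 1.5 points. The simulated SD was about 39, and about 46 in the more-than-proportional row, which lies outside the documented 25.4 to 39.9.

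**5. How to adjust.** A second simulation set rho directly: normal outcome, SD 35, 135 per arm, blocks of 4, 1,500 runs per setting. It compared the planned CMH, a CMH stratified by centre × baseline half, and a CMH on rank residuals.

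| strata | rho | planned | baseline strata | rank residuals |
|---|---|---|---|---|
| 12 | 0 | 92.2% | 90.1% | 92.1% |
| 12 | 0.3 | 91.2% | 91.4% | 93.8% |
| 12 | 0.5 | 92.1% | 94.8% | 96.1% |
| 50 | 0 | 87.0% | 74.0% | 87.0% |
| 50 | 0.3 | 88.6% | 78.5% | 89.7% |
| 50 | 0.5 | 86.3% | 81.8% | 91.5% |

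Type I error was 4.0 to 5.1% for all three. The residual form loses essentially nothing at rho 0. Baseline strata lose about 2 points with 12 strata and 13 points with 50. With 50 strata they remain worse than the planned test even at rho 0.5.

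**The case against.** The strongest reply is that nothing here is an error. The planned test holds its level, its sample size reproduces, and baseline is already in the endpoint. All of that stands.

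The reply also holds that the gain may be nil. This stands too: rho is not documented, and restricting counts to 20–70 and IGA to 4 tends to limit it. The degree of site pooling also moves power more than baseline adjustment does for rho up to 0.3. In step 5 the planned test at rho 0 has 92.2% power with 12 strata and 87.0% with 50.

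A reader might infer three stronger things.

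- **That the trial certainly loses power, or is underpowered.** The documents give no correlation from which to conclude either.
- **That adjustment takes 90% power to 92.5%, worth 270/(1 − 0.09) − 270 = 27 subjects.** That needs rho 0.3, beyond the 0.24 reached in the lesion-count simulation. The 90% starting point also belongs to about 114 per arm, not to the 135 analysed under ITT/LOCF.
- **That any baseline-adjusted CMH is free.** Step 5 shows that adding strata is not.

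On timing, the SAP is dated 12 April 2018, after the planned last subject out in Q1 2018, so a late change of primary test could look data-driven. Protocol 9.1 requires the SAP to be final before database lock and unblinding, and the documents do not date either event. The objection therefore limits when the change may be made. It does not remove the case for it.

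**Conclusion.** The point holds as a modest efficiency improvement. The primary analysis is valid but adjusts only for centre, and it may give up a little power if percent change still depends on baseline count. At 135 per arm and SD 35 the formula gain is about 0.2 to 1.7 points for rho 0.1 to 0.3. In simulated lesion counts it is about 0 to 1.5 points. The downside in power at rho 0 is negligible.

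These sizes rest on assumed correlations and on the simulation settings above. The formula uses a normal approximation, whereas the simulated rank tests start from lower power. The documents support neither a claim of invalidity nor one of a definite power loss.

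**What to change.** Before unblinding, amend protocol 9.1.4 and SAP 6.3.1 as follows.

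1. Within each analysis-centre, compute ridits of percent change and ridits of baseline lesion count.
2. Regress the first on the second with a common slope across centres and treatment not in the model.
3. Apply the same centre-stratified CMH row-mean-score test to the residuals, using them directly as scores.
4. Do this for ITT/LOCF and PP at Week 12 (Table 15), and for Weeks 4 and 8 (Table 16), so that the PP check uses the same test as the primary analysis.
5. Keep the unadjusted CMH as a supportive line in Table 15.
6. Do not add baseline categories to the CMH strata.

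Endpoint, null hypothesis, analysis sets, centre strata and the 5% level are unchanged. No new data or visits are needed.

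The cost is a ranking and a regression step before PROC FREQ, plus a documented protocol amendment. Protocol 11.1 requires that amendment to be submitted to and approved by the applicable IRBs/ECs, and by regulators where required, before it is implemented. If the sponsor prefers not to amend, the minimum is to pre-specify the adjusted test in the SAP as a sensitivity analysis.
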